Hypothesis: TKA will impair whole body and muscle function, in part, through reductions in skeletal muscle fiber size, with preferential atrophy in MHC II sub-types, reduced single fiber tension (force/CSA) and velocity and decreased mitochondrial content and function.

Aim 2: Define the utility of NMES to prevent early, postsurgical skeletal muscle structural and functional adaptations to TKA.

Hypothesis: NMES will lessen TKA-induced muscle fiber atrophy and contractile dysfunction and preserve or increase mitochondrial content and respiration while lessening mitochondrial ROS production.

METHODS AND PROCEDURES

We will use a randomized, controlled design, in which older adult patients with knee OA being evaluated for TKA will be recruited and undergo baseline evaluations (Pre-surgery Testing) prior to surgery. Patients will then be randomized (1:1) to a 5 week intervention of NMES or control (n=32/group, expecting 25% attrition rate to arrive at n=24/group) using a covariate-adaptive approach, which will incorporate age, BMI, sex and surgeon into the randomization scheme. After completing the intervention, they will be re-tested at 5 weeks (5 wk Post-surgery Testing) following surgery. Volunteers can opt into an optional 2 week follow-up testing period. Primary outcomes will be tested at the 5 week evaluation, with 2 wk testing including assessment of ancillary mechanistic hypotheses. Assessment of physical activity by accelerometry (5 d each throughout the 5 week post-surgical period) will monitor variation in physical activity between groups. Each phase of the protocol is described below.

Pre-surgery testing will include assessments of whole muscle size and function, accelerometry to assess habitual weight-bearing activity level, single muscle fiber size and mechanical function and mitochondrial content and function. Detailed descriptions of these assessments are provided below.

Treatment intervention Volunteers will be randomized to NMES or control groups for the 5 weeks following TKA surgery (described below in detail).

5 wk Post-surgery testing will include measurements identical to Baseline Testing, with post-training biopsies performed ≥ 3 d following strength testing/NMES to eliminate any residual effects, per our usual protocol in our past IRB-approved training studies in other clinical populations (heart failure, end-stage knee osteoarthritis).

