2 wk Post-surgery testing (optional) will consist of a skeletal muscle biopsy to assess single muscle fiber size, mitochondrial content and function and anabolic catabolic signaling pathways via standard biochemical/immunolabeling techniques.

6 month Post-surgery testing will include assessments of whole muscle size and function and whole body functional measures to provide data on whether hypothesized preservation in single muscle fiber size/function with NMES will relate to longer-term improvements in whole muscle size/function and whole body functionality.

Procedures:

All of the procedures and interventions on volunteers recruited for these studies are carried out solely for research purposes, as none are part of standard therapy in TKA patients. We will describe procedures that will be performed for each of the Aims.

Aim 1

Primary outcomes, which will be assessed at baseline and 5 wk post-intervention, include: skeletal muscle fiber cross-sectional area (CSA) and function, mitochondrial content, morphology and function and weight-bearing activity. Secondary outcomes include: whole muscle size/function and accelerometry. Procedures that will be performed on volunteers to obtain these primary and secondary outcome measures are described below.

Pre-surgery testing

Percutaneous skeletal muscle biopsy of the vastus lateralis (VL) will be performed on the leg scheduled to undergo TKA, per procedures used by our research group in a range of patient populations, including knee OA patients (1, 2). Tissue will be proportioned for mechanical (single fiber function), immunohistochemical (IHC), mitochondrial functional (oxygen consumption rate and hydrogen peroxide production) and electron microscopy (EM) measurements, with remaining tissue frozen in liquid N₂. The VL was chosen because of its importance in determining functional disability (3) and its structural and functional adaptations to TKA (4). The following measures will be assessed from muscle tissue.

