Statistical Analytical Plan

Project Title:

Skeletal muscle atrophy and dysfunction following total knee arthroplasty

Version Date:

3-23-22

NCT number:

NCT03051984

**Principal
Investigator
(contact):**

[name]

Grant Sponsor:

NIA R01 AG050305

For Aim 1, using pre-surgery and 5 wk post-TKA assessments in the control group, we will assess the effect of TKA (pre- vs. 5 wk post-TKA) on muscle fiber size and function. Primary outcomes include: single muscle fiber CSA for MHC I and IIA fibers and tension and velocity for MHC I and IIA fibers, and IMF and SS mitochondrial content. We will use a general linear mixed model, with a random effect to account for observations clustered within patients (eg, single fiber CSA and function), with the model conceptualized as a multi-level analysis with single fiber values comprising level 1 variables and whole muscle or person-level covariates comprising level 2 variables (130). Covariates (eg, baseline value, etc.) can be included in the model as level 2 variables to determine if variation in any primary outcome is related to variability in these factors. Additionally, we can include sex in the model to examine whether the effects of TKA differ between men and women. In secondary analyses, we will examine whether changes in muscle fiber size or functional mediate changes in whole muscle and body function using mediation analysis, if effects of TKA are noted in the latter. Such analyses seeks to determine whether the effect of an independent variable or intervention (TKA) on some outcome variable (whole muscle/body function) can be transmitted through a third variable, referred to as a mediator (single fiber CSA or function). Variables with multiple observations per subject will be collapsed into a single mean value.

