For Aim 2, pre- and 5 wk post-surgery data will be compared between volunteers randomized to NMES and control interventions. Our primary analysis will assess treatment effects (group X time interaction) on muscle structural and functional variables. Primary outcomes are identical to Aim 1 and will be similarly evaluated using a general linear mixed model, as described above, with group (NMES vs. control) and time (pre vs. 5wks post-TKA) as between- and within-subject factors, respectively. Potential confounding factors will be compared between groups and factors that differ can be included into the model as level 2 covariates. We assume that dropouts will be random, but will examine whether they differ from volunteers completing the study. Moreover, we can conduct sensitivity analysis on dropouts, assuming the most and least conservative responses, to assess their impact on study outcomes. Additionally, we can include sex as an additional effect in these models to determine if NMES effects differ by sex. In secondary analyses, we will also examine the effect of treatment on whole muscle/body functional measures. If there are effects of NMES to maintain whole muscle/body functionality at 5 weeks, we will examine whether changes in single fiber structural or functional outcomes partially or completely mediate whole muscle/body functional improvements with NMES using mediation analysis.

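### The primary mixed model, as written, nests fibres in patients with no biopsy or visit level, so tests of change on six of the eight primary outcomes are too liberal if patients differ in change

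*SAP*

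**What the plan says.** The Aim 1 paragraph of the SAP sets up a general linear mixed model "with a random effect to account for observations clustered within patients (eg, single fiber CSA and function". The levels are described as "with single fiber values comprising level 1 variables and whole muscle or person-level covariates comprising level 2 variables". The Aim 2 paragraph carries the same model over, "with group (NMES vs. control) and time (pre vs. 5wks post-TKA) as between- and within-subject factors, respectively", and makes the group-by-time interaction the primary test.

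The outcomes are listed under Aim 1: "Primary outcomes include: single muscle fiber CSA for MHC I and IIA fibers and tension and velocity for MHC I and IIA fibers", plus IMF and SS mitochondrial content. That is eight primaries, of which six (CSA, tension and velocity, each in two fibre types) are measured on individual fibres.

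The fibres come from separate tissue samples. In the Protocol (Procedures, Pre-surgery testing), "Percutaneous skeletal muscle biopsy of the vastus lateralis (VL) will be performed on the leg scheduled to undergo TKA". Under Methods and Procedures, "5 wk Post-surgery testing will include measurements identical to Baseline Testing", which brings a second biopsy.

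Neither document states a biopsy or visit level, a patient-by-time random effect, a covariance structure for repeated visits, or a degrees-of-freedom method.

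**The concern.** There are three sources of variation in these data: patient, biopsy within patient, and fibre within biopsy. Fibres from one biopsy share whatever is particular to that patient at that visit, both the patient's own response to surgery or NMES and the sampling variation of that piece of muscle. The written model has only the first and third levels.

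A patient intercept adds the same amount to the pre-surgery and 5-week values, so it drops out of the pre/post difference (Aim 1) and the group-by-time difference (Aim 2). What remains as the error term is essentially fibre-to-fibre variance. Measuring more fibres in the same patients then shrinks the standard error almost without limit, although the number of patients has not changed.

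This is harmless only if every patient changes by the same amount and biopsies add no sampling variation. The SAP's own plans sit badly with that condition. It intends to "examine whether changes in single fiber structural or functional outcomes partially or completely mediate whole muscle/body functional improvements with NMES", which has little purpose unless fibre changes differ between patients. It also says "we can include sex in the model to examine whether the effects of TKA differ between men and women", which is weaker support because it is an optional check.

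At stake are false claims of TKA-induced atrophy or contractile loss in Aim 1, and of NMES benefit in Aim 2.

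**Working it through.** **Inputs from the documents.** The Protocol (Methods and Procedures) plans 32 per group and 24 per group after 25% attrition; 24/(1 - 0.25) = 32, so that figure reproduces. Aim 1 uses controls only (N = 24 patients, g = 1 group). Aim 2 uses both arms (N = 48, g = 2). Each patient has two biopsies.

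**Assumptions, because the documents give no figure.** Two-sided 5% tests; m fibres of a given type per biopsy; rho = biopsy-level share of within-patient variance, which is scaled to 1. If biopsies added no sampling variation, rho = 0.10 would correspond to a between-patient SD of true change of sqrt(2 x 0.10) = 0.45 within-patient SDs.

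**Step 1. True variance.** The variance of a biopsy mean about its patient's mean level is rho + (1 - rho)/m = D/m, with D = 1 + (m - 1)rho.

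**Step 2. What the patient-intercept model uses.** With balanced data it pools the fibre and patient-by-time sums of squares:

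- error df = 2N(m - 1) + (N - g). At m = 10, Aim 2: 864 + 46 = 910. Aim 1: 432 + 23 = 455. A patient-by-time error term would have 46 and 23.
- expected error mean square E = [2N(m - 1)(1 - rho) + (N - g)D]/df.

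**Step 3. Ratio of model SE to true SE = sqrt(E/D), Aim 2.**

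| rho | m | D | E | sqrt(E/D) | SE too small by about |
|---|---|---|---|---|---|
| 0.01 | 10 | 1.09 | 0.995 | 0.955 | 4% |
| 0.05 | 10 | 1.45 | 0.975 | 0.820 | 18% |
| 0.10 | 10 | 1.90 | 0.951 | 0.707 | 29% |
| 0.10 | 30 | 3.90 | 0.949 | 0.493 | 51% |

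For rho = 0.10 and m = 10: E = (864 x 0.9 + 46 x 1.9)/910 = (777.6 + 87.4)/910 = 0.951.

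**Step 4. False-positive rate.** To a close approximation this is 2[1 - Phi(1.96 x sqrt(E/D))]. For rho = 0.10 and m = 10: 2[1 - Phi(1.386)] = 16.6%. Simulation of the balanced case (400,000 draws per cell, Aim 2) gives:

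| rho | m = 10 | m = 30 | m = 100 |
|---|---|---|---|
| 0 | 5% | 5% | 5% |
| 0.01 | 6.1% | 8.6% | 16.6% |
| 0.05 | 10.8% | 21.7% | 42.8% |
| 0.10 | 16.5% | 33.3% | 56.4% |

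Aim 1, with 24 controls, agrees within 0.3 points. A t-test on each patient's change in mean holds 5.0% throughout.

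**Step 5. Uneven fibre counts.** REML random-intercept fits (4,000 null trials per cell, Aim 2) with 5 to 15 fibres per biopsy give 5.0%, 5.8%, 10.8% and 15.7% at rho = 0, 0.01, 0.05 and 0.10. With 15 to 45 fibres they give 22.4% and 33.7% at rho = 0.05 and 0.10. The t-test on change in patient means stays at 4.7% to 5.5% in the same trials.

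**Step 6. Which change cures it.** In separate REML fits (400 null trials, m = 10, rho = 0.10), adding a random time effect took the rate from 16.8% to 5.5%. Keeping the intercept-only model but using patient-level df left it at 15.7% in simulation (Aim 2, same m and rho). The missing random term is the fault; the df method alone does not repair it.

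**The case against.** The best defence is that the text is incomplete rather than wrong. It does not say that the random effect is an intercept only. Calling group a between-subject and time a within-subject factor is the language of repeated-measures analysis, where a subject-by-time error stratum is usual. An analyst who coded it that way would have no problem. The SAP also cites a reference for the multilevel approach that is not among the documents, and it might set out further terms.

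That is a fair account of what may have been intended. But the SAP describes one random effect, for clustering within patients, and two levels. An analyst who follows those words gets an invalid test of the primary contrasts, and a reader cannot tell which model was fitted.

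Two other sentences might seem to help. One says that variables with several observations per subject will be averaged. It closes the mediation text, and it cannot govern the primary model, which keeps single fibres at level 1. The other allows baseline value as a covariate. If only 5-week fibres were the outcome, a patient intercept would be the right error term for comparing groups. However, the covariate is optional and does not fit the stated group-by-time test.

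It is also true that the size is not anchored in the documents. CSA is measured by immunohistochemistry, while tension and velocity are measured on skinned fibre segments, so m may differ between outcomes. This limits what can be said about magnitude, not direction.

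**Conclusion.** The concern holds on its stated terms. Read as written, the primary model for both aims has no error term for differences between patients in change. If any such differences or biopsy sampling variation exist, the tests on six of the eight primary outcomes exceed their nominal level. The direction is certain whenever rho is above zero. The size depends on m, rho and alpha, none of which the documents give: over the grid above the Aim 2 rate runs from 5% (rho = 0) to 56.4% (rho = 0.10, m = 100). Even rho = 0.01 matters once many fibres are measured.

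IMF and SS mitochondrial content are affected only if several electron microscopy observations per biopsy enter the model, which the SAP does not say. Because this concerns the validity of the primary tests, it must be settled before analysis.

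**What to change.** State in the SAP, for both aims, that fibres are nested in biopsy (patient by visit) and biopsies in patient. Add a patient-by-visit random effect, or a random time slope by patient, with Kenward-Roger or Satterthwaite degrees of freedom. A simpler alternative is one mean per patient, fibre type and visit, with change analysed at patient level. It is exactly equivalent only when fibre counts are balanced, but it kept its level with uneven counts (Step 5). Say which variables the averaging sentence covers, and whether mitochondrial content enters as one value or several per biopsy. If several, give it the same structure.

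The cost is one or two sentences and one extra random term, with no new data. Confidence intervals will be wider and nominal power lower. The planned 32 per group need not change on this account, but power at 24 completers per group should be justified from the between-patient SD of change. If this structure was intended all along, writing it down costs nothing.

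### The outcome's own baseline, entered as a level 2 main effect in a model that already has the pre-surgery visit in its response, cannot answer the association question and does not adjust the group by time test

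*SAP*

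**What the plan says.** In the SAP's Aim 1 paragraph the data are the two visits of one arm, "using pre-surgery and 5 wk post-TKA assessments in the control group", analysed in a mixed model "with a random effect to account for observations clustered within patients (eg, single fiber CSA and function"). The paragraph then offers covariates, naming the baseline value first: "Covariates (eg, baseline value, etc.) can be included in the model as level 2 variables". Their stated purpose is "to determine if variation in any primary outcome is related to variability in these factors".

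In the Aim 2 paragraph the same primary outcomes "will be similarly evaluated using a general linear mixed model, as described above". Both visits stay in the response, because the design factors are given thus: "with group (NMES vs. control) and time (pre vs. 5wks post-TKA) as between- and within-subject factors, respectively". The test of interest is stated directly: "Our primary analysis will assess treatment effects (group X time interaction"). That paragraph has its own covariate rule, which does not name baseline: "factors that differ can be included into the model as level 2 covariates".

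Nothing in either paragraph restricts the response to the 5-week visit when baseline is a covariate, and nothing crosses a covariate with time.

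**The concern.** Because time has two levels, pre and 5 weeks, the pre-surgery value is half of the response. If the same value is also a patient-level covariate, it partly predicts itself. Three consequences need checking.

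- **Association.** The covariate is offered as a way to learn whether an outcome depends on baseline. A model that regresses baseline on itself in half its rows may report dependence where none exists.
- **Adjustment.** A term that is constant within a patient has no bearing on that patient's change. A report could call the group by time contrast adjusted when it is the unadjusted one. This applies equally to the Aim 2 factors that differ between groups.
- **Standard error.** The covariate distorts the residuals at the two visits in opposite directions, which could make the standard error of the change contrast too small.

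**Working it through.** **Inputs.** From the protocol (Methods and Procedures): 32 randomised per group, 25% attrition, 24 completing. This reproduces: 24/(1−0.25) = 32. It is the only sample-size arithmetic in the documents and does not depend on this point. The documents give no SD, pre/post correlation, fiber count, alpha or power. I therefore assume r from 0 to 0.9, outcome SD 1 at each visit unless stated, a two-sided 5% test on 46 df, and no NMES effect. Simulations use 2,000 to 4,000 trials per setting.

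**Step 1: fitted slope.** Let B be the pre-surgery value and b the true slope of the 5-week value on B. In the pre rows the slope on B is 1 by identity; in the 5-week rows it is b. A main effect averages them: (1+b)/2. With equal variances b = r, giving (1+r)/2.

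**Step 2: group by time estimate.** In complete pairs, change = (5-week value) − (pre value). A term γB, or γ times any patient-level factor, appears in both and subtracts out. With one value per visit the estimate with the covariate equals the estimate without it to 1e-14. Exact cancellation needs balance: complete pairs and, for fiber data, equal fiber counts per visit, as in these calculations.

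**Step 3: standard error, one value per visit, equal variances, complete pairs.**
- Pre residual: B(1−r)/2, with variance (1−r)²/4.
- 5-week residual: −B(1−r)/2 + e, with variance (1−r)²/4 + 1 − r².
- Their covariance is −(1−r)²/4, which is negative, so the estimated patient variance is pushed to its boundary of zero (71% to 100% of simulated trials).
- Mean residual variance: (1−r)(3+r)/4. With zero patient variance the model takes the variance of change as twice this, (1−r)(3+r)/2. The true value is 2(1−r). The ratio is (3+r)/4.
- With 24 per group: true SE = √[2·2(1−r)/24] = √[(1−r)/6]; model SE = √[(1−r)(3+r)/24].

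| r | slope | true SE | model SE | type I error with baseline | without |
|---|---|---|---|---|---|
| 0 | 0.50 | 0.408 | 0.354 | 0.089 | 0.057 |
| 0.3 | 0.65 | 0.342 | 0.310 | 0.073 | 0.046 |
| 0.5 | 0.75 | 0.289 | 0.270 | 0.063 | 0.046 |
| 0.7 | 0.85 | 0.224 | 0.215 | 0.052 | 0.045 |
| 0.9 | 0.95 | 0.129 | 0.127 | 0.050 | 0.049 |

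Slopes and SEs are from the formulas; error rates are simulated.

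**Step 4: other conditions.**
- *Unequal variances, r=0.5:* type I error 0.095 if the 5-week variance is half the pre variance, 0.051 if it is double.
- *Missing 5-week visits (32 per group, 8 per group missing):* 0.107, 0.104 and 0.086 at r = 0.3, 0.5 and 0.7, against 0.055, 0.054 and 0.043 without the covariate. The estimate now moves (by at most 0.26, 0.17 and 0.10 SD in any one trial) but is no more precise: its SD at r=0.5 is 0.289 with the covariate and 0.284 without.
- *Fiber-level model with patient and patient-by-visit effects, r=0.5 (10 to 200 fibers per visit; 0.1 to 0.5 of fiber variance between patient-visits):* the SE shrinks by about 6% to 9%; type I error is 0.056 to 0.081, against 0.042 to 0.057 without.
- *Fiber-level model with only the patient effect named in the SAP, same settings:* the SE is essentially unchanged (0.208 and 0.208 at 10 fibers and share 0.3; largest change 0.393 to 0.392). Type I error is 0.11 to 0.82 with or without the covariate, because patient-by-visit variation is left out.

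**Step 5: sound uses of baseline.** Regressing the 5-week patient mean on group and baseline (ANCOVA; one value per visit, equal variances) returns a slope equal to r within 0.01 and type I error of 0.048 to 0.054 for r from 0 to 0.9. At r=0.5 its SE is 0.251, against 0.287 for the change contrast without a covariate. Adding baseline and baseline by time to the two-visit model gives the ANCOVA estimate to 1e-14, with type I error of 0.049 to 0.054.

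**The case against.** Four points can fairly be made in the plan's defence.

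1. *The covariate is optional and sits in Aim 1.* True. Aim 1 is control-only and has no group by time term, and the stated Aim 2 primary test does not require the covariate. It reaches Aim 2 only through the back-reference to the Aim 1 model. This limits the seriousness, but a plan should still not pre-authorise a form that gives a wrong answer. The algebra also applies to the Aim 1 time effect.

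2. *Including a variable may be shorthand for including its interactions.* The next Aim 1 sentence includes sex in order to see whether TKA effects differ by sex, which needs a sex by time term that is not written out. If baseline by time is likewise intended, the lack of adjustment and the small standard error both disappear. That is a good reason to write the product down; as it stands, the text describes a level 2 variable and no product.

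3. *Baseline value might mean another measure.* The sentence concerns any primary outcome, so the outcome's own baseline is the natural reading. If another measure is meant, Step 1 falls away but Step 2 stands.

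4. *Confounding is limited by design.* Allocation is randomised and covariate-adaptive on age, BMI, sex and surgeon. A reader might infer from Step 2 that the NMES estimate will be biased. The documents do not support that: they give no imbalance, and any bias figure would need an assumed one. What stands is only that the listed remedy, as a main effect, would not work in complete pairs.

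A reader might also infer that the covariate makes the Aim 2 test too liberal in general. That does not follow. For the six fiber-level primary outcomes (CSA, tension and velocity in MHC I and IIA) under the single random effect named, the covariate barely touches the standard error. The excess error there has a different cause.

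**Conclusion.** The point holds in limited form. If the outcome's own baseline enters as a main effect while both visits are in the response, the reported slope is (1+r)/2 under one value per visit and equal variances. It therefore cannot show whether 5-week values depend on baseline. In complete pairs neither this term nor any other patient-level main effect adjusts the group by time contrast. Neither conclusion depends on the size of any NMES effect.

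The standard-error effect is conditional. It arises with one value per visit (mitochondrial content, if analysed that way) or when a patient-by-visit effect is in the model. With one value per visit, equal variances and complete pairs it is modest: about 9% type I error at r=0, which would mean a patient's 5-week value is unrelated to their own baseline, about 6% at r=0.5 and about 5% from r=0.7. It is larger (about 9% to 11% for r from 0.3 to 0.7) when a quarter of 5-week visits are missing. The value of r is not in the documents, so these are ranges, not predictions.

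This is a wording repair that should be made, not a fault in the required primary analysis.

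**What to change.** **Aim 1 paragraph of the SAP.** State that the outcome's own pre-surgery value is a covariate only when the response is the 5-week value (ANCOVA, using patient means for fiber outcomes). Alternatively, state that it enters the two-visit model together with its product with time, centred at its mean so that the time effect keeps its meaning. Otherwise remove it from the two-visit model. Deleting it is not the only remedy.

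**Aim 2 paragraph of the SAP.** State that any retained pre-randomisation covariate enters with its product with time.

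The cost is two sentences and no new data. The ANCOVA form also gains precision: at r=0.5 the SE falls from 0.287 to 0.251, about 13% (1 − 0.251/0.287). These sentences do not cure the missing patient-by-visit variation in the fiber-level model, which needs its own correction.
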